## 2. STUDY SYNOPSIS AND SCHEMA

## Study Synopsis

[figure not shown]
Title	Efficacy of ASIMOMMY® Compared to Domperidone and Placebo in Increasing Breastfeeding: Randomized Single-Blind Controlled Trial in Indonesia.
Purpose	Assessing the efficacy of ASIMOMMY® in increasing breast milk production in postpartum mothers.
Hypothesis	ASI MOMMY® increases milk production in postpartum mothers.
Methodology	
Study Design	Randomized Control Trial (RCT) .
Study Time	October 2022 until March 2022.
Study Location	Tegalrejo and Jetis Primary Health Care, Yogyakarta.
Study Product	
Treatment group	ASI MOMMY®.
Control group:	Domperidone and placebo.
Subject Criteria:	
Inclusion Criteria:	
 
Mothers 20-35 years old.
 
Gestational age at delivery 37-40 weeks.
 
Vaginal delivery.
 
Normal body mass index (BMI 18.5-24.9 kg/m^2).
 
Not taking drugs or breast milk enhancement supplements.
 
Healthy mother's condition with normal nipples (protruding).
 
Healthy baby condition with good suction reflex.
 
The baby consumes only breast milk.
 

Exclusion criteria:	
 
Allergy to ASI MOMMY® and Domperidone.
 
The mother is taking medications that affect the effects of domperidone (such as antacids, cimetidine, ranitidine, famotidine and nizatidine) or medications that interact with domperidone (such as haloperidol, lithium).
 
The mother is in a state of illness requiring hospitalization.
 
Mother has HIV AIDS, heart problems, mastitis, and had undergone breast surgery.
 
Underweight, overweight and obese mothers.
 
Giving birth to twins.
 
The baby has a congenital defect that affects the suctioning process of breast milk
 

	
 
• Infants and mothers who did not participate in the treatment until completion (day 7 of the intervention).
 

Sampel size	The sample size was 15 subjects per group. The total sample size was 45 subjects.
Subject Allocation Method	Randomization with a randomization list.

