### 3. STUDY FLOW CHART OR TIME AND EVENT TABLE

Visit	Screening/ Baseline	Treatment/ Day 0	Day 7	Unscheduled Visit
Visit Window	-14 days	-	+0 –14 days	-
Informed Consent	✓			

Assign subject ID	✓			
Medical History	✓			
Inclusion/ Exclusion Criteria	✓			
Physical Exam (incl. temp, BP, BW)	✓			
Randomization	✓			
Treatment		✓	✓	
Adverse event				

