## 9. STUDY POPULATION

### a. Subject Recruitment

Data collection is done by healthcare providers on duty. Data collection is conducted starting from July 2022 until December 2022 by finding information about mothers in labor from Jfestis and Tegalrejo public health centers. Women in

puerperium who meet the inclusion and exclusion criteria are gathered in the research until the number of samples needed is fulfilled.

The researcher explains the research intent, method, and procedure that will be done to the mother. Then the mother is allowed to sign the informed consent form if they agree to become a research subject. The research subjects are given lactation counseling. Next, the research subjects are randomized by the researcher using the random number table with each group containing 15 subjects. The researcher will allocate each group with one type of treatment, that is drug A, drug B, and drug C, then randomization is conducted. The list of randomizations is kept by the researcher.

b. Populasi

The subject population in this research are postpartum women from Tegalrejo Public Health Center and Jetis Public Health Center in Yogyakarta who plan to breastfeed their baby.

c. Inclusion Criteria

- a. Gestational age 37-40 weeks at labor
- b. Giving birth vaginally
- c. Normal body mass index (BMI 18.5-24.9 kg/m^2)
- d. Does not consume drugs or supplements to enhance breastmilk
- e. Healthy women with normal nipple condition (protrudes)
- f. Condition of baby is health with good suction reflex
- g. Baby currently only consumes breastmilk

d. Exclusion Criteria

- a. Allergy towards ASI MOMMY® and Domperidone
- b. Women who consumes drugs that influences the effects of domperidone (such as antacids, cimetidine, ranitidine, famotidine, and nizatidine) or drugs that interacts with domperidone (such as haloperidol, lithium).
- c. Women who are in sick condition and needs in-hospital treatment
- d. Women with HIV AIDS, heart problems, mastitis, and a history of breast surgery
- e. Underweight, overweight, and obese women
- f. Twin pregnancies
- g. Babies born with a congenital disease that affects the breastfeeding process
- h. Babies and mothers who do not follow the regimen from start to finish (seventh day of intervention)

e. Number of CTP Sites

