## 10. CLINICAL TRIAL PROCEDURE

a. Recruitment and Enrollment

The research team will fill the recruiter information log sheet. All subject candidates will receive starting information and disclose their willingness to participate in the clinical trial and consent to give information about their phone number and home address.

b. Recruitment Plan

Research subject candidates are recruited until the amount of subjects fulfill the minimal sample amount that has been determined by the research team.

c. Initial Subject Screening

During initial screening the screening form will be filled, the researcher will fill the screening log, and if the subject candidate fulfills the inclusion and exclusion criteria of the research, they will be given a subject ID number by the research team.

d. Informed Consent Procedure

Research subjects will be given starting information and be given the opportunity to ask questions if they still have questions regarding the research. After it is made sure that the research subjects have understood and received information about the research, the doctor or midwife on site will ask for the subject's signature for willingness to participate in every step of the research.

e. Baseline Assessment

This study includes interviews related to the demographic data of the subjects.

f. Randomization

Randomization using random numbers that is obtained from the random numbers table. The randomized list is placed inside a non-transparent, sealed envelope and is given serial numbers according to the number of subjects. The envelopes are held by one of the researchers and kept in the Center. Every subject that fulfills the criteria to participate in the research will be reported to the Center and Research Site, and an envelope is taken according to the serial numbers.

g. Treatment

i. Subject Discontinuation Criteria

In this research, the criteria for sample drop out includes subjects/babies who are sick and cannot continue participating in the research, babies who drink baby formula during the intervention, and subjects who consecutively skips consuming the capsules.

Termination of the intervention is done if the subject experiences side effects or serious adverse effects and will be examined by the research doctor for further observation and will receive treatment according to the research flow and placed in the intervention termination form.

ii. Treatment Discontinuation

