Drug administration will end when the patient has completed the research process or the subject is placed under the drop out criteria.

iii. Replacement of Subject

Replacement of research subject is done if the number of subjects that is needed in the research does not fulfill the minimum amount due to drop out or termination of intervention.

iv. Follow-up of Withdrawn Subject

Subjects who withdraw due to heavy allergic reactions will receive monitoring by the research doctor and if the subject withdraws due to other dropout factors then the subject is required to give the product back to the research team.

h. Follow Up

Follow up of research subjects will be done by research assistants by giving periodical reminders of when to take the drug through WhatsApp broadcasting that is given to the research assistants by the subjects.

i. Blinding

i. Type(s) of Blinding

The type of blinding done is single blind, where the researcher knows the type of capsule product given to each respondent, however, the respondent and research assistants or operator who administers the product does not know which type or product is given to the respondent

ii. Maintenance of Blinding

To maintain the blinding, the list of randomization is only kept and known by the researcher.

iii. Breaking the Blinding

The list of randomization will be opened at the end of the research when all the research process is finished.

j. Preventions of the Subject Dropout

To prevent dropout of subjects, the research assistants will periodically remind the subjects when to take the capsules and schedule for next visit.

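### Non-completion to day 7 is listed as an exclusion criterion, so read literally it excludes mothers and infants already randomised and dosed, including those stopped for side effects

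*Protocol*

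**What the plan says.** Section 9.d of the protocol ends its exclusion criteria with item h: "Babies and mothers who do not follow the regimen from start to finish (seventh day of intervention". The synopsis carries the same criterion: "Infants and mothers who did not participate in the treatment until completion (day 7 of the intervention". Neither version is qualified.

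The protocol also fixes when the criteria are applied:

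- In the section 3 flow chart, the row "Inclusion/ Exclusion Criteria" is ticked in the screening/baseline column only.
- In 10.c, a candidate who "fulfills the inclusion and exclusion criteria of the research, they will be given a subject ID number".
- In 10.f, "Every subject that fulfills the criteria to participate in the research will be reported to the Center and Research Site", and the envelope is then drawn in serial order.
- In 8.b, capsules go to subjects who have already been randomised.

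Two further rules bear on item h. Section 10.g.i says "Termination of the intervention is done if the subject experiences side effects or serious adverse effects", and separately lists drop-out for illness, formula feeding and skipped capsules. Section 10.g.iii provides for replacement when the number of subjects "does not fulfill the minimum amount due to drop out or termination of intervention".

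On size, the synopsis states: "The sample size was 15 subjects per group. The total sample size was 45 subjects".

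**The concern.** An exclusion criterion should be answerable when a subject is admitted. Item h depends on what happens during the seven days of treatment, so nobody can answer it at screening. If it is followed at all, it is followed after allocation, and it then removes subjects for an event that treatment itself may have caused.

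A mother stopped for a side effect has not followed the regimen to day 7, so item h covers her, and nothing in item h, the synopsis or 10.g exempts stops for safety. The retained groups could then contain nobody who stopped early, in any arm. Tolerability figures computed on those groups would omit early stops, and the weight-gain comparison would be made among completers instead of among the groups as randomised.

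This is a small pilot whose stated aim is milk production, not safety. Still, 18.e sends the results to the Indonesian regulator, and 6.c hopes the work will support a preparation that is both safe and effective. In arms of 15, one or two early stops are a noticeable part of the tolerability information.

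**Working it through.** **Step 1: order of events.** Setting the sections side by side gives this sequence: screening against the criteria (section 3, 10.c), subject ID (10.c), envelope (10.f), capsules (8.b), then seven days of treatment and the day-7 weighing. Item h can be judged only at the last stage, whereas the protocol judges eligibility at the first. The conflict is internal to the protocol and needs no arithmetic.

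**Step 2: who item h catches.** Stops for side effects under 10.g.i and the drop-outs listed there both leave the regimen unfinished if they occur before the last dose. Both therefore meet item h. Section 10.g.iii names both as grounds for replacement once the minimum is not met.

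**Step 3: is any spare stated?** The plan's figures are 3 × 15 = 45 in total and 22 + 23 = 45 over the two sites. No spare is stated. The 15 itself cannot be reproduced, because 14.b gives no value for the standard deviation. If the three printed means (3426.6, 3221.1, 3000) are taken as the group means, the sum of squares is 91,034. With one-way ANOVA, alpha 0.05 and 80% power, n = 15 then follows for an SD of about 350 to 363 g. It is therefore not known whether 15 is the calculated minimum or already holds an allowance. For example, 13/(1 − 0.10) = 14.4 also rounds up to 15.

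**Step 4: illustration of what could be omitted.** The protocol gives no rate, so 1 to 3 stops in one arm are assumed, each replaced by a subject who completes. With k stops, 15 + k subjects are dosed and 15 are retained. Intervals are exact (Clopper-Pearson) 95%.

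| Stops k | Retained subjects | All dosed | Rate in all dosed | 95% CI |
|---|---|---|---|---|
| 1 | 0/15 | 1/16 | 6.25% | 0.2 to 30.2% |
| 2 | 0/15 | 2/17 | 11.8% | 1.5 to 36.4% |
| 3 | 0/15 | 3/18 | 16.7% | 3.6 to 41.4% |

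For 0/15 the interval is 0 to 21.8%, since 1 − 0.025^(1/15) = 0.218. The zero in the second column follows from how the retained set is defined, so it is not evidence about this trial.

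**Step 5: how likely is at least one early stop?** With an assumed stop rate d, the chance of one or more among the first 15 in an arm is 1 − (1 − d)^15. This is 54% for d = 5% and 79% for d = 10%.

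**Step 6: weight gain.** If a fraction d of an arm is removed and those subjects gain D grams less than the rest, the retained mean exceeds the mean of all randomised by d × D. With assumed values, 10% and 100 g give 10 g, and 20% and 200 g give 40 g. The comparison between arms is distorted only as far as d × D differs between them.

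**The case against.** The strongest reply is that safety handling in this protocol does not depend on completion. Section 15.b records side effects from consent until three days after each subject's own last dose, which covers early stoppers, and puts all of them in the case report form. Section 10.g.i has terminated subjects examined, treated and entered on a termination form. Section 10.g.iv adds medical monitoring after severe allergic reactions, and the appendix holds a log of serious adverse events by subject ID. All of this stands. A reader might infer that side effects in early stoppers are lost, or that a completer-only side-effect table is planned. The documents support neither: replacement does not delete data, and no section prescribes such a table.

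A reader might also infer that the first stop in an arm must trigger replacement because 15 is the minimum. That is plausible but not established. The protocol never says that 15 is the minimum meant in 10.g.iii, the site figures are projections, and the calculation behind 15 cannot be reconstructed.

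Finally, a safety population is commonly left to the statistical analysis plan, which is not at hand. That is fair, and the lack of one here is not the point. A plan that kept all dosed subjects would prevent the loss, but it would then depart from item h as written. The contradiction sits in the protocol and has to be removed there.

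**Conclusion.** The point holds as a fault in a stated rule. Item h, in both places, makes an event after randomisation an exclusion criterion, against the protocol's own screening sequence. Read literally with 10.g.i and 10.g.iii, it excludes randomised and dosed subjects, including those stopped for side effects, and allows their replacement when numbers fall below the minimum.

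The consequence is conditional: only results reported on the retained subjects alone would omit early stops. If results are reported on everyone dosed, nothing is lost. The size is unknown. The 1 to 3 stops per arm, the 5% and 10% rates and the weight-gain shortfalls are assumptions for illustration, and the 0/15 is true by construction. The correction should be made because it is cheap and the arms are small, not because a distorted report has been shown to be planned.

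**What to change.** Delete item h from the exclusion criteria in section 9.d and the matching entry in the synopsis. Section 10.g.i already covers discontinuation, so nothing needed for conduct is lost.

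Add to 10.g.iii, for example: *Subjects who are terminated, drop out or are replaced remain in the trial's data. Side effects, serious adverse events and stops for side effects are reported by randomised arm for all mothers who took at least one dose, and their infants.*

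The cost is a wording change in three places, using data the protocol already collects. The downside for the sponsor is that side-effect rates may look slightly less favourable than among completers alone.

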## 10. CLINICAL TRIAL PROCEDURE

a. Recruitment and Enrollment

The research team will fill the recruiter information log sheet. All subject candidates will receive starting information and disclose their willingness to participate in the clinical trial and consent to give information about their phone number and home address.

b. Recruitment Plan

Research subject candidates are recruited until the amount of subjects fulfill the minimal sample amount that has been determined by the research team.

c. Initial Subject Screening

During initial screening the screening form will be filled, the researcher will fill the screening log, and if the subject candidate fulfills the inclusion and exclusion criteria of the research, they will be given a subject ID number by the research team.

d. Informed Consent Procedure

Research subjects will be given starting information and be given the opportunity to ask questions if they still have questions regarding the research. After it is made sure that the research subjects have understood and received information about the research, the doctor or midwife on site will ask for the subject's signature for willingness to participate in every step of the research.

e. Baseline Assessment

This study includes interviews related to the demographic data of the subjects.

f. Randomization

Randomization using random numbers that is obtained from the random numbers table. The randomized list is placed inside a non-transparent, sealed envelope and is given serial numbers according to the number of subjects. The envelopes are held by one of the researchers and kept in the Center. Every subject that fulfills the criteria to participate in the research will be reported to the Center and Research Site, and an envelope is taken according to the serial numbers.

g. Treatment

i. Subject Discontinuation Criteria

In this research, the criteria for sample drop out includes subjects/babies who are sick and cannot continue participating in the research, babies who drink baby formula during the intervention, and subjects who consecutively skips consuming the capsules.

Termination of the intervention is done if the subject experiences side effects or serious adverse effects and will be examined by the research doctor for further observation and will receive treatment according to the research flow and placed in the intervention termination form.

ii. Treatment Discontinuation

Drug administration will end when the patient has completed the research process or the subject is placed under the drop out criteria.

iii. Replacement of Subject

Replacement of research subject is done if the number of subjects that is needed in the research does not fulfill the minimum amount due to drop out or termination of intervention.

iv. Follow-up of Withdrawn Subject

Subjects who withdraw due to heavy allergic reactions will receive monitoring by the research doctor and if the subject withdraws due to other dropout factors then the subject is required to give the product back to the research team.

h. Follow Up

Follow up of research subjects will be done by research assistants by giving periodical reminders of when to take the drug through WhatsApp broadcasting that is given to the research assistants by the subjects.

i. Blinding

i. Type(s) of Blinding

The type of blinding done is single blind, where the researcher knows the type of capsule product given to each respondent, however, the respondent and research assistants or operator who administers the product does not know which type or product is given to the respondent

ii. Maintenance of Blinding

To maintain the blinding, the list of randomization is only kept and known by the researcher.

iii. Breaking the Blinding

The list of randomization will be opened at the end of the research when all the research process is finished.

j. Preventions of the Subject Dropout

To prevent dropout of subjects, the research assistants will periodically remind the subjects when to take the capsules and schedule for next visit.

## 11. STUDY TREATMENT

a. Study Intervention

i. Active Group

The intervention group is the group of patients who receive ASI MOMMY® preparation.

1. Dose, Formulation, Rute, Duration, Hours, etc

ASIMOMMY® formula contains extracts of Katuk leaf (Sauvopis androgynous) 300 mg, Fenugreek (Trigonella foenum-graceum) 50 mg, and Moringae oleifera extract (Moringa leaf) 50 mg. The formulation is taken once a day at nighttime, as much as 2 capsules for a duration of 7 days ([name] et al., 2020). The capsule is taken once a day at nighttime at 20.00 as much as two capsules.

ii. Control group

The positive control group consists of patients who receive domperidone

1. Dose, Formulation, Route, Duration, Hours, etc

Domperidone that is used is 10 mg dosage, taken every 8 hours for 7 days (Paul et al., 2015). The drug is taken three times a day at 06.00, 14.00, and 22.00 West Indonesia Time.

iii. Placebo group

The negative control group consists of patients who receive placebo.

1. Dose, Formulation, Route, Duration, Hours, etc

Sugar inside the capsule does not give any therapeutic effect, is taken once a day, as much as 2 capsules, for duration of 7 days.

b. Dispense of Study Medications

At the first visit, research subjects are given all the drugs equivalent to the number of capsules that will be consumed for a week.

c. Drug Packaging/handling/Storage/Accountability

ASI MOMMY® is a polyherbal formula that is made in a capsule form by the herbal drug industry (PT Swayasa Prakarsa, Yogyakarta, Indonesia). This drug preparation is kept under 30 degrees celsius in a dry place away from sunlight.

Each capsule contains extracts of Katuk leaf 300 mg, Fenugreek 150 mg, and Moringa leaf 50 mg. ASI MOMMY® has undergone activity testing and acute and subchronic toxicity testing. Research has shown that ASI MOMMY® formula works actively as an herbal galactogogue drug and does not have give any toxic effects, therefore it is safe to be given to humans (unpublished data).

d. Training procedure

Training will be given by experts provided by the research team to the research members in two sites which includes materials about the SOP, protocols, and entire research flow.

## 12. CONCOMITANT THERAPY

a. General Considerations

The subjects are prohibited from consuming drugs other than what is provided by the researchers, because it may affect the mechanism or interaction of the intervention drug.

b. Medications Prohibited Before or During the Trial

The types of drugs prohibited during the research among others are antacids, cimetidine, ranitidine, famotidine and nizatidine, or drugs that interact with domperidone such as haloperidol and lithium.

### 13. STUDY ASSESSMENT

In this research, the assessments done are regarding physical examination, measurement of blood pressure, along with the baby's body weight prior to and after the intervention.

### 14. STATISTICAL ANALYSIS

a. General Design

The method used in this research is a single blind, Randomized Control Trial (RCT). The benchmark of this study is the measurement of the babies' weight before and after the intervention therapy that is given (the research product).

i. Hypothesis

**H0:** The traditional drug preparation ASIMOMMY® does not increase breastmilk production in postpartum women.

**H1:** The traditional drug preparation ASIMOMMY® increases breastmilk production in postpartum women.

ii. Output (*Endpoint*)

The output expected is that ASI MOMMY® is able to increase the production of breastmilk which in turn increases the weight of the baby after the mother receives the intervention.

b. Rationale for Sample Size and Statistical Power

Sample size is calculated using sample size formula for hypothesis testing on the average of more than two groups, unpaired numeric comparative in one measurement, are as follows (Dahlan, 2016):

$$z_{\beta} = \frac{\sqrt{v_2(2[v_1+\delta^2]^2-[v_1+2\delta^2])} - \sqrt{v_1(v_1 + \delta^2)(2v_2 - 1)F}}{\sqrt{v_1}(v_1 + \delta^2)F + v_2(v_1 + \delta^2)}$$

Information:

$n$  = number of subjects in one group

$Z_{\beta}$  = beta standard value 20 % which is 0,84

$V_1$  = degree of freedom from the number of =  $k-1$ .  $V_1 = 3-1 = 2$

$V_2$  = degree of freedom from the number of groups  $k$  ( $n-1$ ).  $V_2 = 3(n-1)$

$K$  = number of groups = 3

$$\delta^2 = \frac{n \sum (x_i - \bar{x})^2}{s^2}$$

$X_i$  = average of baby body weight in a group

$X_1$  = average of baby body weight in the domperidone and placebo group which is 3426,6 (Amri *et al.*, 2020)

$X_2$  = average of baby body weight in the placebo group which is 3221,1 (Amri *et al.*, 2020)

$X_3$  = average of three groups is 3000

$X$  = overall average (3 group)

$S$  = combined standard deviationn

$F$  = Anova table value as function of type 1,  $V_1, V_2$

Alpha = type 1 error 0,05.

i. Projected Number of Site

Locations used in this study are two sites which are Jetis and Tegalrejo Public Health Centers in Yogyakarta.

ii. Projected Number of Participant per site

Total number of subjects in one place is around 22 or 23 subjects.

c. Statistical Methods for primary and Secondary Outcomes

Statistical data analysis in this study is done using SPSS 24.0 program. The data undergoes normality testing first to determine which statistical analysis test will be used. The result of research with categoric data will be presented in the form of quantity/frequency and percentage from each group. Numeric data with normal distribution (parametric) will be presented in the form of average and standard deviation, whereas if the data is not distributed normally (non-parametric) then it will be presented using median, minimal value and maximum value.

d. Significance Testing

Chi-squared test is used for variables with categoric data (nominal and ordinal). Bivariate analysis test that is used for variables with numeric data (parametric) is the One Way Anova test with Post Hoc Bonferroni, meanwhile for non parametric data is Kruskall Walis with Post Hoc Mann Whitney.

Analytical test for variables aside from parametric data and dependent variables is using Pearson correlation, while non-parametric data is analysed using Spearman correlation

e. *Demographic and baseline Characteristics*

Research data with categoric data (nominal and ordinal) is presented in the form of quantity/frequency and percentage from each group.

f. *Safety Analysis*

The entire data analysis process will be done by a biostatistics expert appointed by the research team.

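### The 80%-power calculation in section 14.b uses infant body weights instead of 7-day gain, mislabels two of its means, names no ASI MOMMY mean and gives no SD, so 15 per group is unsupported and cannot be reproduced

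*Protocol*

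**What the plan says.** Protocol section 14.b uses a formula for comparing means in more than two unpaired groups, with k = 3, v1 = 2, v2 = 3(n − 1), alpha 0.05 and "beta standard value 20 % which is 0,84". The inputs are described as follows:

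- X1: "average of baby body weight in the domperidone and placebo group which is 3426,6"
- X2: "average of baby body weight in the placebo group which is 3221,1"
- X3: "average of three groups is 3000"
- X, on its own line: "overall average (3 group", with no value
- S: "combined standard deviationn", with no value

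The section prints no solution for n. Fifteen per group appears in the synopsis (section 2) and in section 9.a. Section 14.b.ii adds only a projection of 22 or 23 subjects at each of two sites, which totals 45.

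The synopsis defines the outcome as the infant's weight on day 7 of the intervention minus the weight on day 0. For numeric data, section 14.d plans "One Way Anova test with Post Hoc Bonferroni" or, if the data are not normal, "Kruskall Walis with Post Hoc Mann Whitney". Section 8.a calls the trial a pilot.

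**The concern.** Four things separate the printed inputs from the stated sample size.

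1. **Wrong variable.** The means are body weights and the outcome is a within-infant change over seven days. The SD of a change is not the SD of a weight, so the effect-size term is on the wrong scale. Section 14.b does not say at what age the cited weights were taken.
2. **X1.** Its label covers domperidone and placebo, yet placebo has its own mean, X2.
3. **X3.** It is labelled as an average over three groups, yet the overall mean is a separate symbol. No mean is attributed to ASI MOMMY, the product under test.
4. **S.** Without a value the formula cannot be solved.

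Fifteen per group is the number that section 9.a randomises to. It is also evidently the minimum that sections 10.b and 10.g.iii recruit and replace dropouts to. With no planned difference in gain and no SD, a reader cannot tell what effect the trial was sized to detect. A null result cannot then be read as informative or otherwise, and a positive one cannot be set against a planned effect.

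**Working it through.** The plan's own figure of 15 cannot be reproduced, because S is missing. What can be done is to ask which S would return 15 under each reading of the label on X3.

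**Method.** Exact one-way ANOVA power from the noncentral F distribution with df 2 and 3(n − 1), alpha 0.05 and noncentrality λ = n·Σ(xi − x̄)²/S². The formula printed in section 14.b is not relied on, because its denominator may have been damaged when the PDF was read.

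**Reading 1: 3426.6, 3221.1 and 3000 are the three group means.**

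- x̄ = (3426.6 + 3221.1 + 3000)/3 = 3215.9
- Deviations: 210.7, 5.2, −215.9
- Σ(xi − x̄)² = 44,394 + 27 + 46,613 = 91,034
- S giving exactly 80% power: 349.8 at n = 14 and 363.1 at n = 15

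So 15 is the smallest adequate n only for 349.8 < S ≤ 363.1. Check at n = 15, S = 363.1: λ = 15 × 91,034/363.1² = 10.36, which gives 80% power. For other values of S (assumptions for illustration; the protocol gives none):

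| Assumed S (g) | Smallest n per group | Power at n = 15 |
|---|---|---|
| 300 | 11 | 93% |
| 400 | 18 | 71% |
| 450 | 23 | 61% (0.605) |

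Under this reading 3000 belongs, by elimination, to ASI MOMMY. It lies 3221.1 − 3000 = 221.1 g below placebo, the opposite direction to H1.

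**Reading 2: 3000 is the overall mean, as its label says.**

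- Third group mean = 3 × 3000 − 3426.6 − 3221.1 = 2352.3
- Deviations: 426.6, 221.1, −647.7
- Σ(xi − x̄)² = 181,988 + 48,885 + 419,515 = 650,388
- S giving exactly 80% power: 935.0 at n = 14 and 970.6 at n = 15

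**Comparison.** The S needed for n = 15 differs between the readings by √(650,388/91,034) = 2.67. At the same S of 363 g, Reading 1 gives 15 per group and Reading 2 gives 4.

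**What 15 per group delivers on the gain scale, in SD units.** These figures apply to the ANOVA/Bonferroni branch of section 14.d only.

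- Omnibus test: 80% power needs λ = 10.36, so f = √(λ/45) = √(10.36/45) = 0.48.
- Pairwise test at alpha 0.05/3 with 42 df: the critical t is 2.494. By noncentral t, 80% power needs a difference of 1.22 SD, or 122 g for each 100 g of SD of gain.
- Half-width of the simultaneous 95% interval: 2.494 × √(2/15) = 0.91 SD.

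The protocol gives no SD of gain, so these cannot be turned into grams without an assumption. They do not cover the Kruskal-Wallis/Mann-Whitney branch.

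**The case against.** The strongest reply is that the notation settles the reading. Section 14.b defines Xi as a group mean and lists the overall mean separately, so X3 is probably the third group's mean with a slipped label. An S near 360 g then returns exactly 15. That makes Reading 1 the more natural one. It does not supply S, and it leaves the test product below placebo. The direction does not affect n, since the F test uses squared deviations. It does show that the planning scenario is not the hypothesis being tested. Reading 2 remains what the label literally says.

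Second, under randomisation the expected difference in day-7 weight equals the expected difference in gain, so body-weight means could serve for the difference and mainly the SD would be wrong. That stands as a possibility only, because the section does not say when the weights were measured.

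Third, the type I error of the planned tests does not depend on planning assumptions, and an interval for the difference can be read whatever S was assumed. That is correct. What is lost is the ability to judge the result against a planned effect.

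Fourth, this is a pilot. Section 8.a says so, and that could justify 15 per group by itself. It does not rescue a formal 80%-power calculation whose inputs are wrong as printed.

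**Conclusion.** The concern holds. The alpha 0.05, 80%-power rationale in section 14.b rests on the wrong variable, two faulty labels, no ASI MOMMY mean and an S without a value. Fifteen per group follows only if S lies in a narrow band that the protocol does not state: about 350 to 363 g under one reading, about 935 to 971 g under the other. Both bands assume exact ANOVA power with equal groups.

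This does not show that the trial is underpowered. The documents give neither a mean nor an SD of 7-day gain, so true power could be above or below 80%. The harm is to the justification of the sample size and the interpretation of the result, and the number enrolled need not change. It should be fixed.

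**What to change.** Keep 45 subjects and rewrite section 14.b in one of two ways.

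- **Keep a power statement.** Replace the body weights with a named mean 7-day gain for each of ASI MOMMY, domperidone and placebo, and a sourced SD of gain. Correct the labels of X1 and X3. State what 15 per group gives under the ANOVA/Bonferroni branch: 80% power for an omnibus f of about 0.48 and for a pairwise difference of about 1.22 SD, with a simultaneous 95% interval half-width of about 0.91 SD. Note that these figures do not cover the non-parametric branch.
- **Drop the power statement.** Remove the 80% claim and justify 15 per group as the size of the pilot that section 8.a describes.

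The cost is rewriting one section, with no extra subjects. Under the first option, the restated power may prove better or worse than 80%.
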